The reference start date for safety assessments (e.g. adverse event onset, laboratory abnormality occurrence, vital sign measurement, dose interruption, etc.) is the start of study treatment.

The reference start date for all other, non-safety assessments (e.g. molecular response, disease progression, ECOG performance status, patient reported outcomes (PRO), etc.) is the date of randomization.

The reference start date for dose escalation (200 mg q.d.) is the date when a subject starts first escalated dose.

The study day will be displayed in the data listings. If an event starts before the reference start date, the study day displayed on the listing will be negative.

Time unit

A year length is defined as 365.25 days. A month length is 30.4375 (=365.25/12) days. If duration is reported in months, duration in days will be divided by 30.4375. If duration is reported in years, duration in days will be divided by 365.25.

A week length is defined as 7 days. If duration is reported in weeks, duration in days will be divided by 7.

Baseline for the treatment period

For efficacy evaluations, the last non-missing assessment, including unscheduled assessments on or before the date of randomization is taken as “baseline” value or “baseline” assessment. In the context of baseline definition, the efficacy evaluations also include PRO and performance status.

For safety evaluations, the last available assessment, including unscheduled assessments before the date of start of study treatment is taken as “baseline” assessment.

For pre-dose electrocardiogram (ECG), the last available assessment before the treatment start date is used for baseline.

For ECGs requiring triplicate measures per time point, the average of these measurements will be reported by sites in eCRF baseline.

For mutations, the screening/baseline assessment is taken as “baseline” assessment.

In rare cases where multiple laboratory measurements meet the baseline definition, with no further flag or label that can identify the chronological order, then the following rule should be applied: If values are from central and local laboratories, the value from central assessment should be considered as baseline.

If subjects have no value as defined above, the baseline result will be missing.

On-treatment assessment/event and observation periods

For adverse event reporting the overall observation period will be divided into three mutually exclusive segments:

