If more than one assessment is assigned to the same time window, the assessment performed closest to the target date will be used for by-visit statistical analyses. If 2 assessments within a visit window are equidistant from the target date, then the average of the 2 assessments will be used. If multiple assessments are on the same date, then the the average will be used. Data from all assessments (scheduled and unscheduled), including multiple assessments, will be listed.

Table 2-1 Time windows for molecular response

Assessment	Target day of assessment	Time Interval
Baseline	≤ 1	\leq Day 1 [#]
Week 12	85	Day 2 to day 127
Week 24	169	Day 128 to day 211
Week 36	253	Day 212 to day 295
Week 48	337	Day 296 to day 379
Week k (k=60, 72, ...)	$K \times 7 + 1$	Day $k \times 7 - 40$ – $k \times 7 + 43$

Day 1 = Date of randomization
EOT assessments are mapped to the time points as needed.

Table 2-2 Time windows for cytogenetic response

Assessment	Target day of assessment	Time Interval
Baseline	1	≤ Day 1 [#]
Week 48	337	Day 253 to day 420
EOT [*]	EOT	EOT

[#] Day 1 = Date of randomization. Should bone marrow assessments have been performed before the main informed consent is signed but within 56 days of Week 1 Day 1, no further bone marrow sampling will be required at screening and local assessment data will be collected.

^{*} Only required for Early Discontinuation due to lack of response / loss of response

For PRO data time windows will be defined for descriptive summary by visit. If more than one assessment is available in the same time window, the assessment closest to the planned date will be considered. If two assessments are obtained with the same time difference compared to the scheduled visit day, the assessment obtained prior to visit will be considered.

Table 2-3 Time windows for PRO: MDASI-CML

Assessment	Target day of assessment	Time Interval
Baseline	1	≤ Day 1 [#]
Week 4	29	Day 2 to day 57
Week 12	85	Day 58 to day 127
Week 24	169	Day 128 to day 253
Week 48	337	Day 254 to day 421
Week 72	505	Day 422 to day 589
Week 96	673	Day 590 to day 757
Week 120	841	Day 758 to day 925
EOT (Week 144)	1009	Day 926 to day 1009

[#] Day 1 = Date of randomization

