The general rule for the target day of assessment and time interval is: For Week k visit, target day of assessment is defined as $k*7+1$. For the time interval, “Lower limit” = “upper limit of prior applicable visit” +1. “Upper limit” = “target day of current visit” + integer part of (“target day of next applicable visit” – “target day of current visit”)/2.

Last contact date

The last contact date will be derived for subjects not known to have died at the respective analysis data cut-off date using the last complete date among the following:

Table 2-4 Last contact date data sources

Source data	Conditions
Date of randomization	No condition
Start/End dates from further antineoplastic therapy	Non-missing medication/procedure term
Start/End dates from drug administration record	Non-missing dose. Doses of 0 are allowed
Study disposition date	The date of the subject's last protocol assessment performed in the study phase
Any specific efficacy (molecular or cytogenetic) assessment date if available	Evaluation is marked as 'done'
Laboratory/PK collection dates	Sample collection marked as 'done'
Vital signs date	At least one non-missing parameter value
Performance status date	Non-missing performance status
Start/End dates of AE	Non-missing verbatim term

The last contact date is defined as the latest complete date from the above list on or before the respective data cut-off date. The cut-off date will not be used for last contact date, unless the subject was seen or contacted on that date. No date post the cut-off date will be used. Completely imputed dates (e.g. the analysis data cut-off date programmatically imputed to replace the missing end date of a dose administration record) will not be used to derive the last contact date.

The last contact date will be used for censoring of subjects in the analysis of overall survival.

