2.6.1.1 Molecular response

MMR rates at all scheduled data collection time points, i.e., the protocol-planned visits except for 48 weeks which is already covered by primary endpoint. Such rates are defined as the proportion of subjects with MMR at the respective time points.

MMR rates by all scheduled data collection time points, i.e., the protocol-planned visits. These are cumulative MMR rates by time points and are defined as the proportion of subjects who achieve MMR at or before specified visits, i.e. if a subject achieves an MMR but then loses it before or at a specific visit, he/she will still be classed as achieving MMR by that specific time point. Subjects without any documented response for which an evaluable response assessment was never provided will be considered as non-responders for the period of time up to that time point.

Molecular response category at specific time points, i.e., the protocol-planned visits. Categories of molecular response are defined in Appendix.

Molecular response category by specific time points, i.e., the protocol-planned visits. This is defined as the molecular response category up to the specific time points.

Time to MMR (in weeks) is defined as: $(\text{date of first documented MMR} - \text{date of randomization} + 1)/7$.

Duration of MMR is defined in protocol section 8.3.1.1 as the time from the date of first documented MMR to the earliest date of confirmed loss of MMR, progression to accelerated phase (AP) or blast crisis (BC), or CML-related death. Loss of MMR and progression to accelerated phase (AP)/blast crisis (BC) are defined in Appendix.

The duration of MMR (in weeks) is calculated as: $(\text{end date or censoring date of MMR} - \text{date of first MMR} + 1)/7$.

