2.6.2 Statistical hypothesis, model, and method of analysis

No statistical testing of secondary efficacy endpoints will be performed .

Molecular response at and by time points

- Molecular Response MMR rate at weeks 12, 24, 36, 72, 96 and 144
- MMR rate at week 48 for subjects with MMR at baseline
- Rate of MR4 and MR4.5 at weeks 12, 24, 36, 48, 72, 96 and 144
- Rate of BCR::ABL1 $\leq 10\%$ and $\leq 1\%$ at Weeks 12, 24, 36 and 48
- Rate of BCR::ABL1 $\leq 10\%$, BCR::ABL1 $\leq 1\%$, MMR, MR4 and MR4.5 by all-time points

Frequency and percentage of all molecular response categories (defined in [Appendix](#)) using FAS or FAS 2 will be presented for each time point.

For each endpoint above, the rate and the associated 95% confidence interval based on the Clopper-Pearson method will be presented. For the at-time-points summary, subjects discontinuing the treatment prior to a specific time point due to any reason or subjects without an available assessment at that time point will be considered as non-responders for that time point. For the by-time-points summary, subjects without any documented response for which an evaluable response assessment was never provided will be considered as non-responders for the period of time up to that time point.

The cumulative incidence of MMR will be graphically displayed by an increasing step function. This curve will increase each time (after randomization) at which a new responder is observed and thus will increase up to the best observed response rate (e.g. up to 50% if half of the subjects in the analysis population are able to achieve response).

Additional chromosomal abnormalities and occurrence of high-risk ACAs

The number and percentage of subjects achieving MMR at week 48 and week 96, and CCyR at week 48 will be presented by ACA status at baseline. Per NCCN 2024 guideline and ELN 2020 guideline, the major route ACA/Ph+ including trisomy 8, isochromosome 17q, second Ph, trisomy 19, and chromosome 3 abnormalities are considered as presence of ACA at baseline.

Time to MMR

Time to MMR is defined in protocol Section 8.3.1.1 and calculated as: date of first documented MMR - date of randomization +1. Descriptive statistics (minimum, maximum, median, quartiles, mean, SD) of time to MMR will be provided.

The FAS will be also used to perform similar Time-to-Event analyses as described below for duration of MMR.

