For subjects in the FAS who have not experienced any MMR, the time will be censored as follows in the Kaplan-Meier analysis:

- If a subject does not achieve the specified response before the cut-off date for the analysis, censoring time will be the last molecular assessment (PCR) date on treatment prior to the cut-off date or the EoT visit, whichever comes first.
- If a subject discontinues study treatment prior to achieving a response for a reason other than disease progression or death, then the subject will be censored at the last molecular assessment (PCR) date on treatment prior to the cut-off date or the EoT visit, whichever comes first.
- If a subject discontinues study treatment prior to achieving a response due to progression or death, then the censoring time will be set to the longest follow-up time in the treatment group, that is, consider the response is impossible to reach.
- In case no on-treatment response assessment was performed, the subject will be censored at day 1.

The estimated cumulative incidence rates and 95% confidence intervals at 12, 24, 48, 72, 96 and 144 weeks will be presented. The cumulative incidence curve will be plotted.

Duration of MMR

Duration of MMR is defined in protocol Section 8.3.1.1 as the time from the date of first documented MMR to the earliest date of confirmed loss of MMR, progression to AP or BC, or CML-related death. The time will be censored at the last molecular assessment (PCR) date while on treatment for subjects who have not experienced any of the above events. The duration of MMR will be analyzed for the subjects in FAS who achieve MMR at any time.

Duration of MMR will be analyzed by K-M method and presented by K-M plots. The survival distribution of duration of MMR will be estimated using the Kaplan-Meier method, and Kaplan-Meier curves, medians and 95% confidence intervals [[Brookmeyer and Crowley 1982](#)] of the medians, along with the proportion of subjects who are still in MMR at 24, 48, 72, 96 and 144 weeks and the associated 95% confidence intervals, will be presented.

Duration of MR4 without loss of MMR will be analyzed in a similar fashion to the analysis of duration of MMR.

The additional subjects who were intolerant to the last TKI and were in MMR already at baseline will be assessed for the duration of MMR using FAS 2.

CCyR rates at time points

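### The week-k landmarks for the cumulative incidence of MMR fall one day before the Week k target PCR, so they omit MMRs first seen on or after the target day

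*SAP*

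**What the plan says.** SAP Section 2.6.2 (Time to MMR) defines the time in days: "calculated as: date of first documented MMR - date of randomization +1". SAP Section 2.6.1.1 gives the same quantity in weeks ("Time to MMR (in weeks) is defined as" that difference plus one, divided by 7), and SAP Section 2.1.1 fixes the unit: "A week length is defined as 7 days". The curve is then reported at fixed times: "The estimated cumulative incidence rates and 95% confidence intervals at 12, 24, 48, 72, 96 and 144 weeks will be presented".

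The PCR schedule uses the same origin. A footnote to Table 2-1 reads "Day 1 = Date of randomization", and the general rule is: "For Week k visit, target day of assessment is defined as" 7k + 1. Table 2-1 also gives a wide window around each visit, for example "Day 296 to day 379" for Week 48, but Section 2.1.1 introduces these windows for by-visit summaries. Neither Section 2.6.2 nor Section 5.6.2 applies them to event times or shifts the landmarks.

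For duration of MMR, Section 2.6.2 reports "the proportion of subjects who are still in MMR at 24, 48, 72, 96 and 144 weeks". Section 2.6.1.1 uses the same plus-one rule for duration, and duration of MR4 is to be analyzed in the same way.

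**The concern.** The event-time formula and the visit calendar are one day apart. Time in weeks is study day divided by 7, so the k-week landmark closes at the end of Day 7k. The Week k PCR is due on Day 7k + 1.

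One day matters because PCR is scheduled only every 12 weeks (Protocol Table 8-2), and the curve steps only when a new responder is documented. Missing a visit by a day can cost that visit's whole increment. Week 12 is the first scheduled PCR after baseline, so the 12-week estimate is the most exposed.

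The same report will also give cumulative MMR rates by scheduled visit (SAP Section 2.6.1.1), and those include the visit in question. A reader would see two different figures for MMR by Week 12, and part of the difference would come only from the definitions.

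**Working it through.** **Inputs.** Event time, week length, origin and target day: SAP Sections 2.1.1, 2.6.1.1 and 2.6.2. Permitted visit days: Protocol Section 8, ±2 days up to Week 12 and ±7 days from Week 24 to end of treatment.

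**The plan's own figures.** 7k + 1 for k = 12, 24, 36 and 48 gives Days 85, 169, 253 and 337, which match Table 2-1.

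**Timing of an on-target PCR.** Time = study day/7 = (7k + 1)/7 = k + 1/7 weeks. The k-week landmark counts times up to and including k, that is Day 7k or earlier.

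| Landmark (weeks) | Target day | Time (weeks) | Permitted days | Days counted |
|---|---|---|---|---|
| 12 | 85 | 12.14 | 83–87 | 83–84 (2 of 5) |
| 24 | 169 | 24.14 | 162–176 | 162–168 (7 of 15) |
| 48 | 337 | 48.14 | 330–344 | 330–336 (7 of 15) |
| 72 | 505 | 72.14 | 498–512 | 498–504 (7 of 15) |
| 96 | 673 | 96.14 | 666–680 | 666–672 (7 of 15) |
| 144 | 1009 | 144.14 | 1002–1016 | 1002–1008 (7 of 15) |

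**Gap between randomization and first dose.** The table assumes first dose on the day of randomization. Protocol visits run from Week 1 Day 1, whereas event time runs from randomization. The documents give no typical gap. For assumed gaps of 1, 2, 3 and 7 days, the days counted fall to 1, 0, 0 and 0 of 5 at Week 12, and to 6, 5, 4 and 0 of 15 at later visits.

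**Illustration.** Assumed cumulative MMR of 12, 25, 30 and 34% by the Week 12, 24, 36 and 48 visits, no censoring, and first dose on the day of randomization.

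- *All visits on target:* each landmark shows the value from the preceding PCR visit, so 0% (not 12%), 12% (not 25%) and 30% (not 34%) at 12, 24 and 48 weeks.
- *Visits spread evenly over the permitted days:*
  - 12 weeks: 12 × 2/5 = 4.8%
  - 24 weeks: 12 + (25 − 12) × 7/15 = 18.1%
  - 48 weeks: 30 + (34 − 30) × 7/15 = 31.9%

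**Duration.** A loss dated 168 days after first MMR has duration (168 + 1)/7 = 24.14 weeks. It falls just after the 24-week landmark, and the patient is counted there as still in MMR.

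**The case against.** The strongest reply is that little depends on these numbers. No secondary efficacy endpoint is tested. The primary endpoint uses the Week 48 window (Days 296 to 379), and the by-visit cumulative rates already give the clinically natural quantity with Clopper-Pearson intervals. All of this stands, and it limits the importance of the point.

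It could also be said that 12 weeks simply means the Week 12 visit, Day 85. That may be the intention, but the SAP supplies a formula in weeks and no rule linking landmarks to visits. Followed as written, it gives the lower figure.

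Three stronger readings are tempting, and the documents do not support them:

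- *Every MMR first seen at a visit is lost.* A visit held at least one day early is counted if dosing began on the day of randomization, so a landmark usually loses part of the visit's new responders.
- *The offset explains the whole disagreement with the by-visit rates.* Section 2.6.2 censors non-responders who discontinue for reasons other than progression or death, while the by-visit rates keep patients without a documented response in the denominator. The two would differ even with aligned landmarks.
- *Duration of MMR is read a full visit too early throughout.* Duration is the difference between two visit dates, each with its own window, so some losses at a nominal 24-week interval fall at 24.00 weeks or less and are counted. The event is confirmed loss, with confirmation 4 to 6 weeks later (SAP Section 5.4.1), and the SAP does not say which sample dates it. If it is the confirming sample, the 24.14-week example does not apply directly.

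**Conclusion.** The mismatch is real and follows from the SAP's own definitions. A k-week landmark omits every MMR first seen at a Week k PCR done on or after its target day, so the cumulative incidence estimates are biased low.

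In the illustration, the shortfall at 12, 24 and 48 weeks is 12, 13 and 4 percentage points with all visits on target. With an even spread it is 7.2, 6.9 and 2.1 points. The response rates and visit patterns are assumptions; the one-day offset and the counts of permitted days are not. The effect is largest at Weeks 12 and 24 in this illustration, and it grows with any gap between randomization and first dose. No figure is offered for Weeks 72, 96 and 144, where the shortfall depends on how many MMRs are first seen at those visits.

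For duration of MMR and of MR4, the offset acts in the direction of overstating the proportion still in response, but its size cannot be stated until the date of loss is defined. The point should be corrected, but it does not bear on the primary conclusion.

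**What to change.** In SAP Section 2.6.2, do one of the following for time to MMR:

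1. Assign each first MMR to its Table 2-1 mapped visit week before estimation. Treat censoring dates in the same way, so that a patient censored at a visit stays at risk for events mapped to it. This uses the same windows as the by-visit rates. The price is that an MMR seen at an unscheduled PCR as late as Day 127 counts at Week 12.
2. Keep actual dates, read the curve at the end of the protocol visit window (Days 87, 176, 344, 512, 680 and 1016, plus an allowance for the gap between randomization and first dose), and label the results by Week k.

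Reading only one day later, at Day 7k + 1, would still miss late in-window visits. Reading at the upper limits of Table 2-1 fails at Week 144: that limit is 144 × 7 + 43 = Day 1051, past the last permitted end-of-treatment visit on Day 1016.

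For duration of MMR and MR4, state whether loss is dated at the first or the confirming sample, and compute the landmarks from mapped visit weeks without the one-day offset. Moving each duration landmark 6 weeks later is not a substitute: it would put the last one at 150 weeks, beyond the 144-week maximum treatment period.

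The cost is a few sentences in the SAP and a small programming change. No additional data are needed.

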8.1 Screening

Molecular pre-screening

Not applicable.

Screening

Written informed consent must be obtained before any study specific medical procedures are performed.

All screening/baseline assessments (with the exception of cytogenetic assessment of Bone Marrow Aspirate) should occur within 28 days before Week 1 Day 1.

The screening visit window for cytogenetic assessment Bone Marrow Aspirate (BMA) is 56 days prior to Week 1 Day 1. Should bone marrow assessments have been performed before the main informed consent is signed but within 56 days of Week 1 Day 1, no further bone marrow sampling will be required at screening and results from prior bone marrow assessment will be collected. At Week 48, and at end of treatment for patient completing trial for lack of efficacy, a bone marrow aspirate must be collected even if the screening/baseline bone marrow aspirate sample was not collected.

During the screening visit, inclusion and exclusion criteria will be assessed. Screening assessments to confirm eligibility must be performed prior to study enrollment. The results of the central real time quantitative polymerase chain reaction (RQ-PCR) and the local cytogenetic assessment (BMA, performed locally within 56 days of Week 1 Day 1) must be available prior to enrollment and first dose of study treatment. Central mutation analysis will be performed during the course of the study and data not available prior to enrollment.

Screening assessments include: demographics, laboratory baseline assessments (including hematology, chemistry, coagulation, serum pregnancy test and hepatitis markers), physical examination including extramedullary involvement, peripheral blood collection for BCR-ABL1 RQ-PCR, bone marrow aspirate for cytogenetic assessment (if prior bone marrow aspirate evaluation was more than 56 days before Week 1 Day 1) and CCI [REDACTED]. Other assessments includes performance status, ECG, echocardiogram, height, weight and vital signs, as well as evaluation of all relevant medical history including cardiovascular risk factors, CML disease history including T3151 mutation status, prior TKI therapy and antineoplastic medication. Assessment of prior and concomitant medication must be performed prior to the first dose of study treatment. For details of assessments required during screening please refer to [Table 8-1](#).

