1. ***pre-treatment period:*** from day of subject’s informed consent to the day before first administration of study treatment
2. ***on-treatment period:*** from date of first administration of study treatment to 30 days after date of last administration of study treatment (including start and stop date).
3. ***post-treatment period:*** starting at day 31 after last administration of study treatment.

If dates are incomplete in a way that clear assignment to pre-, on-, post-treatment period cannot be made, then the respective data will be assigned to the on-treatment period.

Safety summaries (tables, figures) on the corresponding Safety set include only data from the on-treatment period with the exception of baseline data which will also be summarized where appropriate (e.g. change from baseline summaries). In particular, summary tables for adverse events (AEs) will summarize only on-treatment events, with a start date during the on-treatment period. In addition, a separate summary for death will be provided.

However, all safety data (including those from the pre-treatment and post-treatment) will be listed and flagged as appropriate.

Efficacy summaries on the FAS and FAS 2 (apart from OS and PFS) include data from baseline up to either the last assessment on or before the End of Treatment (EoT) visit or before or on treatment failure, whichever is the earliest.

The efficacy assessments collected post-treatment failure or post-EoT visit are not included in any efficacy analyses (except for OS and PFS analyses). However, they will be listed and flagged as appropriate.

Windows for multiple assessments

Data such as molecular response, cytogenetic response collected over time (including unscheduled visits) will be summarized by scheduled time point. As subjects do not always adhere to the visit schedule, visits will be remapped according to visit windows defined in Tables 2-1 to Table 2-3 of this document to enable by-visit analysis. Only those protocol-defined visits will have the visit window defined. Each assessment (including the end of treatment assessment), either scheduled or unscheduled, will have a mapped visit assigned, as long as study day is available, according to the defined visit window up to the date with data included.

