2.2 Analysis sets

The subject population for the study includes subjects resistant or intolerant to 2 or more prior TKI treatments without MMR at baseline, and an additional group of subjects who were intolerant to the last TKI and were in MMR at baseline. Note that the YR data domain from IRT will be used to identify the stratification groups for the study population, and the biomarker data (B1 domain) containing BCR::ABL ratio will be used to confirm the MMR status at baseline for all subjects. If there is discrepancy between YR and B1 data, the MMR status at baseline will be assessed based on the B1 data.

The Analysis Sets are stated as follows:

Full Analysis Set

The Full Analysis Set (FAS) comprises all participants to whom study treatment has been assigned by randomization except the additional subjects who were intolerant to the last TKI and were in MMR at baseline.

Full Analysis Set 2

The Full Analysis Set 2 (FAS 2) comprises only the additional subjects who were intolerant to the last TKI and were in MMR at baseline and to whom study treatment has been assigned by randomization.

Safety Set

The Safety Set (SAF) includes all participants who received at least one dose of study treatment except the additional subjects who were intolerant to the last TKI and were in MMR at baseline.

Safety Set 2

The Safety Set 2 (SAF 2) includes only the additional subjects who were intolerant to the last TKI and achieved were in MMR at baseline and who received at least one dose of study treatment.

Unless otherwise stated, the analysis sets will be applied as below:

- For the subjects resistant or intolerant to 2 or more prior TKI treatments without MMR at inclusion to the trial
 - The FAS will be used for demographics and baseline characteristics (except disease characteristics) and all efficacy analyses including PROs
 - The SAF will be used for baseline disease characteristics, exposure and all safety analyses
- For the additional subjects who were intolerant to the last TKI and were in MMR at baseline
 - The FAS 2 will be used for demographics and baseline characteristics (except disease characteristics) and selected efficacy analyses including PROs
 - The SAF 2 will be used for baseline disease characteristics, exposure and selected safety analyses

Withdrawal of Informed Consent

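### Duration of MMR in FAS 2 has no time origin of its own; read literally, it starts at the pre-treatment screening PCR and adds up to 4 weeks in which no loss of MMR can be counted

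*SAP*

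**What the plan says.** SAP 2.6.2 defines duration of MMR as "the time from the date of first documented MMR to the earliest date of confirmed loss of MMR"; the other end events are death from CML and transformation to AP or BC. SAP 2.6.1.1 gives the formula: end or censoring date minus date of first MMR, plus 1, divided by 7. The analysis is set out for FAS patients who reach MMR at any time. The same section then extends it to the second cohort, whose members "in MMR already at baseline will be assessed for the duration of MMR using FAS 2". No other origin is stated there, in Protocol 8.3.1.1 or in Protocol 12.5.1.

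The following passages fix what the first documented MMR is for this cohort:

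- SAP 2.2: FAS 2 "comprises only the additional subjects who were intolerant to the last TKI and were in MMR at baseline". Study PCR data "will be used to confirm the MMR status at baseline for all subjects".
- SAP 2.1.1: the efficacy baseline is "the last non-missing assessment, including unscheduled assessments on or before the date of randomization is taken as" baseline. Efficacy summaries on FAS and FAS 2 "apart from OS and PFS) include data from baseline up to either the last assessment" by the end-of-treatment visit or treatment failure.
- Protocol 8.1: screening assessments other than the bone marrow "should occur within 28 days before Week 1 Day 1". The central RQ-PCR result must be in hand before enrollment and first dose.
- Protocol summary and Table 8-2: after screening, the next scheduled PCR is at Week 12.
- SAP 5.4.1: loss of MMR requires a rise of at least 5-fold from the lowest value reached on study treatment.

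**The concern.** The rule suits the FAS, where MMR is reached on asciminib and its first documentation is an on-treatment event. In FAS 2 the response was reached on an earlier TKI, and the study only documents that it is present at screening. A clock that starts there includes days before asciminib was given.

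Those days are event-free by construction. A patient not in MMR at baseline is not in FAS 2, and the loss criterion refers to a nadir on study treatment, which does not exist before the first dose. The added time differs between patients and enters event times and censored times alike.

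Protocol 4.5 gives the rationale for this cohort: a switch to asciminib should carry little risk of losing the response already attained. Time before the switch does not bear on that. Time to MMR, TTF, PFS and OS all start at randomization; duration of MMR does not.

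**Working it through.** **The plan's own figure.** The documents give no figure for this analysis. Their one design figure concerns the primary test in the FAS, and it reproduces: with N = 156 the critical count is 47, exact one-sided alpha is 0.0241 and power at 33% is 80.1%, against the stated 80%. The present point does not touch it.

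**Lead time.** The screening window is Day -28 to Day -1, so the sample precedes Week 1 Day 1 by 1 to 28 days: 1/7 = 0.14 to 28/7 = 4.0 weeks. I take randomization to fall on Week 1 Day 1.

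**Single records**, using the SAP formula:

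| Screening PCR | End date | From screening PCR | From randomization |
|---|---|---|---|
| Day -21 | loss, Day 85 | (84+21+1)/7 = 15.1 wk | 85/7 = 12.1 wk |
| Day -28 | loss, Day 337 (Week 48) | (336+28+1)/7 = 52.1 wk | 337/7 = 48.1 wk |
| Day -28 | still in MMR, Day 1009 (Week 144) | (1008+28+1)/7 = 148.1 wk | 1009/7 = 144.1 wk |

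The last patient is credited with 148.1 weeks in a study whose maximum treatment is 144 weeks.

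**Landmarks.** With a 28-day lead, the 24, 48, 72, 96 and 144-week landmarks refer to 20, 44, 68, 92 and 140 weeks after Day 1. The pre-treatment share is 4/24 = 16.7% at the first and 4/48 = 8.3% at the second.

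**Effect on the proportion still in MMR.** The documents give no loss rate for this cohort, so 5%, 10% and 20% per year are assumptions. The simulation used 400,000 patients per rate, exponential loss, PCR every 12 weeks, visit days spread evenly over the permitted windows (±2 days at Week 12, ±7 later), no dropout, and loss dated at the visit that detects it. At 48 weeks:

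| Loss per year | Randomization origin | Lead uniform on 1 to 28 days | Lead 28 days | Excess at 28 days |
|---|---|---|---|---|
| 5% | 95.95% | 96.44% | 96.50% | 0.55 points |
| 10% | 91.90% | 92.83% | 92.94% | 1.04 points |
| 20% | 83.70% | 85.46% | 85.67% | 1.97 points |

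**Dependence on event dating.** The SAP counts confirmed loss, with a confirming sample 4 to 6 weeks later, and does not say which of the two dates is used. If it is the confirming sample, the 48-week proportion does not move:

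- A loss found at Week 36 has at most (252+7+42+28+1)/7 = 47.1 weeks on the screening clock, so it counts by 48 weeks on either clock.
- A loss found at Week 48 has at least (336-7+28+1)/7 = 51.1 weeks on the randomization clock, so it counts on neither.

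Individual durations are still lengthened.

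**The case against.** The strongest reply is that the SAP never names the screening PCR as the FAS 2 origin. That is so: the origin follows from the definition, the baseline rule and the PCR schedule taken together. Two other readings exist. Starting at the first post-baseline MMR would normally mean Week 12 and would shorten durations. It would also leave a patient who has lost MMR by Week 12 and never regains it without a start date. A Day -28 and a Day 85 origin differ by (28+84)/7 = 16 weeks for the same patient. Starting at a historical MMR on the earlier TKI would add a lead with no limit. The data-from-baseline rule and the use of study PCR data favour the screening sample, and no reading removes the need to state the origin.

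The second reply is that little depends on it. FAS 2 also has the Week 48 MMR rate and response categories by visit, with windows counted from randomization. The endpoint is untested, one patient in 30 is 3.3 points, and 12-weekly PCR is coarser than the lead. All of this stands and limits the weight of the point.

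Two stronger inferences are tempting, and the documents do not support them:

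- A reader might infer that a repeat PCR during screening moves the origin earlier still. Baseline is the last assessment on or before randomization and efficacy data run from there, so a repeat shortens the gap.
- A reader might infer that losses found at a landmark visit are missed only because of the screening origin. A loss on the Week 24 target day gives 169/7 = 24.14 weeks from randomization and falls after the 24-week landmark on either clock. Only visits made early differ, and how many depends on assumed screening and visit days.

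**Conclusion.** The point holds as a defect in the FAS 2 time origin. Followed literally, the SAP lengthens every FAS 2 duration of MMR by the gap from screening PCR to Day 1, at most 4.0 weeks, with no possibility of a counted loss in that gap. The direction is certain under that reading.

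The size is modest. The 48-week proportion is overstated by about 0.5 to 2 points under assumed losses of 5 to 20% per year, a 28-day lead for everyone, and loss dated at the detecting PCR; it is unchanged if loss is dated at the confirming PCR. The analysis is descriptive, secondary and limited to up to 30 patients. The primary analysis and all FAS results are unaffected.

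**What to change.** In SAP 2.6.2, state that for FAS 2 the duration of MMR in weeks is (event or censoring date - randomization date + 1)/7. Apply the same origin to duration of MR4 without loss of MMR for FAS 2 patients already in MR4 at baseline, because SAP 2.6 plans that objective for FAS 2 and SAP 2.6.2 analyses it in the same way. Keep the first-documented-MMR origin for the FAS.

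The cost is one sentence and a one-line programming change, with no new data. The downside is that reported FAS 2 durations become up to 4 weeks shorter.
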